#### Objective 3:

Characteristics will be described by means of large-scale characterisation. The top 10 of disease codes and top 10 of drug codes will be described in the report to simplify dissemination. Pre-specified comorbidities and concomitant medications will also be reported within specific time windows (see "8.6.3. Other covariates"). The number of patients initiating high- or low-doses of NOMAC and CMA (assessed separately) and the number of years since meningioma diagnosis will also be described.

Results will be reported overall and stratified by study period (pre- vs. postintervention).

#### Objective 4:

For each participant initiating treatment with NOMAC or CMA, we will retrospectively assess the occurrence of records indicating the use of other drug classes of interest not containing NOMAC or CMA. This assessment will be performed from the day before index date to the earliest of the start of the study period or the start of the observation period for each patient. We will describe the order in which treatments of interest were prescribed, as first vs. non-first treatments. NOMAC and CMA will be assessed separately.

NOMAC and CMA will be assessed separately. Results will be reported overall and stratified by study period (pre- vs. postintervention), dose (high- vs. low-dose products), and indication (non-HRT vs. HRT). Dose and indication will be assessed at index date (i.e. date of treatment initiation with NOMAC or CMA). Please see "11. Limitations" for more information.

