## 8.4 Follow-up

For the population-level DUS (objective 1), study participants in the denominator population will start contributing person time on the latest of the following: 1) study start date (1st January 2010, or as defined according to the database), 2) date on which they turn 10 years old, 3) date at which they have a year of prior history recorded. Participants will stop contributing person time at the earliest date of the following: 1) end of available data in each of the data sources, 2) date at which their observation period ends (e.g. loss to follow-up, death).

For the patient-level DUS (objective 2 to 5), participants will be followed up from the day of incident prescription of medication (index date), until the earliest end of data availability, date at which their observation period ends (e.g. loss to follow-up, death), or 180 days after ending treatment (objective 5). For objective 2, 4 and 5, index date will be defined as the date of the first-ever prescription of NOMAC or CMA. For objective 3, this will be defined as the date of the first-ever prescription of any of the 6 drug classes of interest (see "8.6.2 Outcomes").

For objective 4, line of treatment will be assessed retrospectively by looking at prior records of alternative treatments, from the date of initiation of treatment with products containing NOMAC or CMA to start of the study period (1st January 2010, or as defined according to the database).

For objective 6, follow-up will be the same as that for objective 1.

Information on the operational definition of index date is described in **Table 4**. Please note that, for objectives 1 and 6, each drug class of interest will be assessed separately, with the washout window specific to the drug class being studied (e.g., when studying NOMAC, the washout window will be applied with respect to this substance only). For objective 3, the washout will be applied to all the drug classes of interest combined.

Authors: [name], [name], [name], [name], [name]

Version: V4.0

**Dissemination level:** Public

Table 4. Operational definition of time 0 (index date) and other primary time anchors.

Study population names	Time Anchor Description (e.g. time 0) 	Number of entries 	Type of entry	Washout window	Care Setting 	Code Type 	Incident with respect to

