#### **Covariates for stratification:**

Covariates for stratification will vary across objectives and will include:

- Age group:
   10-17, 18-34, 35-49, 50-64, +65 years.
- Indication:

Non-HRT vs. HRT. Indication will be assessed using age as a proxy (non-HRT in women aged 10-49 years, HRT in women aged >50 years).

- Dose:
  - High- vs low- dose, for NOMAC or CMA only. For NOMAC, high doses will include amounts from 3.75mg to 5mg. For CMA, high doses will include amounts from 5mg to 10mg. Low doses will be any amounts less than those specified.
- WHO 5th ATC level codes:
  - For NOMAC or CMA only, if counts allow. For NOMAC codes included will be: G03AA14, G03DB04, G03FB12. For CMA, codes included will be: G03AA15, G03AB07, G03DB06, G03FB03.
- Time period:
  - Preintervention: from start date to October 2022; Postintervention: from February 2023 to study end.

See below which covariates apply according to each objective.

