#### Objective 2-5:

For objectives 2 to 5, SMD of each of the covariates for the comparison of drug users in the pre-RMM and post-RMM period as a measure of the impact of the profile of drug users. These covariates will include: duration and cumulative dose (objective 2), patient characteristics (objective 3) and line of treatment (objective 4). For patient characteristics, only conditions will be compared, with the assessment window set as any time prior to 1 day before the index date. For objective 5, covariates will include the proportion of patients diagnosed with meningioma during treatment, and the proportion of patients who discontinue or switch to alternative treatments (assessed separately).

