#### **Databases:**

In IQVIA LPD Belgium and IQVIA DA Germany, the observation period of the patients in these databases is calculated based on the last visit, observation or interaction of the patient with the health care system. This methodology impacts the individuals considered "at risk" for the different medicines of interest of the study (i.e., the individuals included in the denominator populations) during the latest months of available data from the latest data lock, where healthy and/or non-frequent users of the health care system will not be considered active. Consequently, the denominators that will be used to calculate the incident use of drugs in the population may present an artefactual decrease whilst the incident users will remain, incrementing the incidence and prevalence ratios. The presence of these artefacts will be considered when interpreting the results. However, this is likely to affect the amount of follow up available for the study. We expect that the data from the last 6 months may not accurately reflect actual figures of use and, therefore, will be excluded from the analysis for Objective 1 and 6.

Regarding the study period, NAJS will provide data from 2017 onwards only, as prior data might include information on duplicated patients. IQVIA LPD Belgium will provide data from 2012 onwards.

Since information on drug exposure end dates is unavailable in NAJS, treatment duration will not be inferred directly from the start and end dates of drug exposure. Instead, we will infer the treatment period using only the drug exposure start dates, assuming continuous drug exposure between consecutive start dates, if separated by less than 90 days. To account for the final prescription, we apply a 30-day window following the last recorded drug start date. This approach might lead to some uncertainty regarding the exact duration or cumulative dose prescribed.

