The cumulative dose and line of treatment for products containing NOMAC or CMA will be assessed based on exposures recorded during the study period. This assessment will ensure the quality of the data being used, as data collected before 2010 might be inconsistently reported in some data patterns. While this could lead to an underestimation of the cumulative dose or an inaccurate assessment of the line of treatment, we believe this will have a very limited impact on the study, given that we will cover over 12 years of follow-up.

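### Objective 4 searches back to a fixed calendar date, so post-RMM initiators have more searchable history (up to about twice as much) and the first-line share can fall with no change in prescribing; the word *earliest* in the same sentence conflicts with two other sections.

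*Protocol*

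**What the plan says.** A new user of NOMAC or CMA is first-line if no alternative drug class is found in her earlier records. The protocol bounds that search in three ways:

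- 8.8, Objective 4: "from the day before index date to the earliest of the start of the study period or the start of the observation period".
- 8.4 Follow-up: "from the date of initiation of treatment with products containing NOMAC or CMA to start of the study period". The abstract uses the same bound.
- Section 11, Medications of interest: line of treatment "will be assessed based on exposures recorded during the study period", because "data collected before 2010 might be inconsistently reported in some data patterns".

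The strata in 8.6.3 are "Preintervention: from start date to October 2022; Postintervention: from February 2023 to study end". Line of treatment is compared between them by SMD (8.8, Objective 2-5), and Tables 1 and 11 expect fewer first-line initiators after the restrictions. Section 11 accepts that line of treatment may be inaccurate, but adds: "we believe this will have a very limited impact on the study, given that we will cover over 12 years of follow-up". It also records that "NAJS will provide data from 2017 onwards only" and that Belgium starts in 2012.

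**The concern.** Whether a prior alternative is found depends on how far back one can look. Here the far end of the search is a calendar date common to everyone, while the two groups compared sit at opposite ends of the calendar. In calendar time, every post-period initiator can be searched further back than any pre-period initiator. A longer search finds more prior use, so the share classed as first-line drifts down as the database ages.

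That is the direction of the stated hypothesis, and avoiding first-line use of high-dose products is one of the measures being evaluated. Stratifying by dose or indication leaves the look-back unequal. A drop in the first-line share could be read as an effect of the RMM when part of it is database age.

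**Working it through.** **Inputs from the protocol.** Study start: 1 January 2010 (Germany), 2012 (Belgium), 2017 (NAJS), the last two taken as 1 January. Data locks (Table 3): 30-09-2023, 31-12-2023 and 17-11-2023. Pre stratum ends 31 October 2022; post begins 1 February 2023. At least 365 days of prior visibility (8.5).

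**Assumptions, not in the protocol.** Initiations evenly spread within each stratum; alternatives recorded at a constant rate *h* of 2%, 5% or 10% per year in both periods, so prescribing does not change.

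**1. The protocol's own figure.** Study start to October 2022 is 12.8 years in Germany, so over 12 years holds there. It is 10.8 years in Belgium and 5.8 in NAJS, where it does not. In any case this is the length of the pre-period, not the history available to the women who initiate within it.

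**2. Mean calendar look-back with the study-start bound.** For index dates uniform on [a, b] and study start s, the mean is (a + b)/2 − s. Germany pre: 12.83/2 = 6.41, or (1 + 12.83)/2 = 6.91 if initiations begin one year after study start. Germany post: (13.08 + 13.74)/2 = 13.41.

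| | Pre (y) | Post (y) | Ratio |
|---|---|---|---|
| Germany | 6.4-6.9 | 13.4 | 1.9-2.1 |
| Belgium | 5.4-5.9 | 11.5 | 1.95-2.1 |
| NAJS | 2.9-3.4 | 6.5 | 1.9-2.2 |

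**3. Artefact if all women are observed since study start.** First-line share = mean of exp(−hL) over the stratum. Germany at 5%, initiations from study start: 73.8% pre, 51.1% post, a fall of 22.7 points. SMD = (post − pre)/√{[p₁(1−p₁) + p₂(1−p₂)]/2} = −0.48.

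| Fall in points | h = 2% | h = 5% | h = 10% | SMD |
|---|---|---|---|---|
| Germany | 11-12 | 21-23 | 27-30 | −0.28 to −0.64 |
| Belgium | 10-11 | 19-21 | 26-30 | −0.27 to −0.62 |
| NAJS | 6-7 | 12-14 | 19-24 | −0.19 to −0.50 |

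**4. Artefact with patient turnover.** Each woman's look-back is capped at 1 year plus an exponential time of mean 2, 4 or 8 years, so mean prior observation is 3, 5 or 9 years before truncation at study start. Initiations run from study start in Germany and from one year later in Belgium and NAJS.

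| | Ratio at 3 / 5 / 9 y | Fall at h = 5% (points) | Fall over h = 2-10% (points) |
|---|---|---|---|
| Germany | 1.20 / 1.39 / 1.63 | 2.1 / 5.0 / 9.8 | 0.9-14.0 |
| Belgium | 1.15 / 1.34 / 1.56 | 1.6 / 4.4 / 8.6 | 0.7-12.4 |
| NAJS | 1.28 / 1.49 / 1.66 | 2.6 / 5.3 / 7.9 | 1.2-12.8 |

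The SMDs run from −0.03 to −0.29.

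**5. The word *earliest*.** For a woman observed before study start, it admits the older records that 8.4 and section 11 leave out; German records go back to 1992 (8.2). For a woman who enters later, it names a date at which she has no data. Read literally, the maximum German means are 24.4 and 31.4 years, ratio 1.29. Correcting the word alone therefore raises the German calendar ratio to 1.9-2.1, so the two changes belong together.

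**6. After a fix.** With an equal fixed look-back the ratio is 1 and this artefact is zero. If instead the pre stratum is cut to the Objective 2 window (October 2021 to September 2022), the calendar ratio is 1.10 (Germany), 1.13 (Belgium) and 1.24 (NAJS), with a residual fall of about 2-7 points. Under the turnover in step 4, the ratio is 1.00-1.16 and the fall at most about 4 points.

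**The case against.** The strongest objection concerns size. A reader might infer from step 2 that look-back really is twice as long after the RMM. The protocol does not support that: records exist only within each woman's observation period, whose length is not given. Belgium's counts (1.1M cumulative, 213k active) suggest 213k × 12 / 1.1M ≈ 2.3 years per patient if the active count is stable. Initiators, who need at least a year of history, would have somewhat more, but the real Belgian ratio is probably well below 2. A national registry such as NAJS may come closer to its maximum. The recording rates are also assumed. All of this stands, and it is why the turnover range is given.

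A reader might also infer that early pre-period initiators have almost no history. The 365-day rule prevents that in Belgium and NAJS; less than a year of searchable time is possible only in Germany, and only under the study-start bound.

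Objective 4 is descriptive and carries no test, and section 11 does admit misclassification. But the protocol states a directional hypothesis and fixes an SMD, and section 11 does not say that the error differs by period.

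Finally, the Objective 3 SMDs take conditions "with the assessment window set as any time prior to 1 day before the index date", so their look-back also lengthens with calendar time. It would be tempting to move them to one year. The protocol does not support that: its target in Table 11 is any prior meningioma, and a one-year window would miss older diagnoses. There the bias also runs against the hypothesis.

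**Conclusion.** The concern holds in direction; its size is uncertain. The protocol fixes a calendar bound, strata at opposite ends of the calendar and an SMD between them, so the first-line share can fall without any change in prescribing, as the hypothesis predicts. The look-back ratio is at most about 1.9-2.2 under the study-start bound, and about 1.15-1.66 if mean prior observation is 3-9 years. The corresponding artefact is 6-30 points and about 1-14 points, for recording rates of 2-10% per year. Turnover and rates are assumptions. They change the size but, in these scenarios, not the direction.

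This does not show that an observed fall would be wholly artefact, only that the planned comparison cannot separate the two. The 12-year argument does not answer the point and is wrong for Belgium and NAJS. The *earliest* wording is a separate, smaller conflict that can add records only in Germany.

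**What to change.** 1. In 8.8, Objective 4, change *earliest* to *latest*, in line with 8.4 and section 11.
2. For the pre/post SMD on line of treatment, use one fixed look-back in both periods: 365 days, plus a longer window such as 3 years among women with that much history. In Germany, start the compared pre stratum one year after study start so that the window does not reach before 2010. Keep the full look-back as description. Alternatively, restrict the pre stratum to the recent Objective 2 window, which removes most of the inequality but not all.
3. In section 11, replace the claim of very limited impact with a statement that look-back differs by period and by database.
4. For Objective 3, keep the any-time SMD, state that its look-back also differs by period, and show beside it the SMD for the [-365, -1] window already planned in Table 9.

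The cost is a window parameter, one word and a few sentences. A short fixed window counts some women with older alternative use as first-line, in both periods alike. The 3-year window leaves out early initiators, in NAJS those before 2020.

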## Objective 2:

Treatment duration will be reported for the first prescribed treatment. Duration will be derived from the start and end of the prescription.

Cumulative dose will be calculated considering all treatments containing NOMAC or CMA recorded during the study period. If two eras with different doses are separated by less than 30 days, the time between the two eras will be considered as exposed by the first era (Figure 1, first row). If two eras start at the same date, the overlapping period will be considered exposed by both.

[figure not shown]

Figure 1. Gap era joint mode

Cumulative dose and treatment duration will be calculated for all treatments initiated during the study period and occurring over one year before and after the intervention to compare time periods of equal duration. The pre-intervention period for comparison will span from October 2021 to September 2022,

Authors: [name], [name], [name], [name], [name]

Version: V4.0

Dissemination level: Public

the year prior the request for PRAC to review current evidence on NOMAC and CMA. The post-intervention period for comparison will span from February 2023 to January 2024. For databases with less available data (see Table 3) we will limit the comparison to 6 months (post-intervention: February to July 2023; pre-intervention: February to July 2022). Time periods for comparison will cover the same calendar months in case seasonality is detected.

NOMAC and CMA will be assessed separately. Results will be reported overall and stratified by study period (pre- vs. postintervention) and indication at first use (non-HRT vs. HRT).

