#### A. Primary analysis

Hypothesis:	Objective 1: Not applicable, descriptive analysis.
	Objective 2: Cumulative dose and duration of treatments with NOMAC or CMA will be lower after the implementation of restrictions.
	Objective 3: The number of new users of NOMAC or CMA with prior history of meningioma will be reduced after the implementation of restrictions.
	Objective 4: The number of users initiating NOMAC or CMA as first-line treatment will be reduced after the implementation of restrictions.
	Objective 5: The number of discontinuations and switches from NOMAC or CMA to other drug classes will increase after the implementation of restrictions.
	Objective 6: The incidence of NOMAC or CMA will be reduced after the implementation of restrictions, especially for high-dose products. This reduction will not be observed for other drug classes of interest.
Exposure contrast:	Objective 1: Not applicable, descriptive analysis.
	Objective 2: Pre-intervention (1-year period) vs. Post-intervention (1-year period)
	Objective 3 to 6: Pre-intervention vs. Post-intervention
Outcome:	Objective 1: Incidence rates and prevalence of drug classes of interest
	Objective 2: Cumulative dose and treatment duration of NOMAC or CMA.

Authors: [name], [name], [name], [name], [name]

Version: V4.0

Dissemination level: Public

	Objective 3: Number and characteristics of users of drug classes of interest.
	Objective 4: Line of treatment when initiating NOMAC or CMA.
	Objective 5: Diagnosis with meningioma during treatment. Discontinuations and switches
	from treatments with NOMAC or CMA to others.
	Objective 6: Incidence rates of NOMAC or CMA.
	Drug classes of interest, NOMAC and CMA will be assessed separately.
Analytic software:	R
Model(s):	Objective 1: Not applicable, descriptive analysis.
	Objective 2 to 5: Standardised mean differences.
	Objective 6: Segmented regression (Poisson models).
Confounding adjustment method	
	Stratification.
Missing data methods	
	The absence of a record for a condition or medication will be considered as the absence of the disease or use of the medication.
Subgroup Analyses	
	Objective 1: Age groups, indication, study period. For NOMAC or CMA only: dose, WHO ATC 5 th level (if counts allow). A subgroup analysis will be performed restricting the study population to individuals with a prior history of meningioma.
	Objective 2: Study population, indication, study period.
	Objective 3: Study period.

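### Objective 4's look-back has no fixed length and is longer for post-restriction starters, so the first-line share can fall without any change in prescribing

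*Protocol*

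**What the plan says.** Section 8.8, Objective 4, searches from the day before the index date "to the earliest of the start of the study period or the start of the observation period for each patient" for other study classes that contain neither NOMAC nor CMA, and reports each starter as first or non-first. Section 8.4 describes the same search differently: "from the date of initiation of treatment with products containing NOMAC or CMA to start of the study period". The abstract also ends it at the study start, but begins it the day before index. None of these places sets a length. The 365 days of prior data required in section 8.5 are a minimum.

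Section 8.6.3 defines the strata: "Preintervention: from start date to October 2022; Postintervention: from February 2023 to study end". Table 11 gives the contrast: "Objective 3 to 6: Pre-intervention vs. Post-intervention". Section 8.8 makes the comparison by SMD. Only Objective 2 restricts its periods, in order "to compare time periods of equal duration".

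Section 11 says that cumulative dose and line of treatment "will be assessed based on exposures recorded during the study period". It concedes that line of treatment may be inaccurate, but adds: "we believe this will have a very limited impact on the study, given that we will cover over 12 years of follow-up". The same section states that "NAJS will provide data from 2017 onwards only, as prior data might include information on duplicated patients" and that the Belgian data start in 2012.

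**The concern.** First-line status here means that nothing was found, so it depends on how far back one can look. A woman who starts soon after a database opens has about a year of searchable records, or less within the study period in Germany; one who starts in 2023 may have six to almost fourteen. Some earlier treatment that is invisible for the first woman is visible for the second.

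The pre-period stratum mixes short and long windows, while the post-period stratum contains only the longest. The resulting misclassification differs between the groups being compared, and it lowers the first-line share after the restrictions. Table 11 hypothesises a change in that direction, so a fall could be read as an effect of the risk minimisation measures when part or all of it comes from the search window. Stratifying by dose or indication does not equalise the windows.

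**Working it through.** **1. The protocol's own figure.** Section 11 relies on more than 12 years. Starts are January 2010 (section 8.3), 2012 and 2017 (section 11; 1 January assumed). Data locks are from Table 3.

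| Database | Start to end October 2022 | Start to data lock |
|---|---|---|
| Germany | 12.8 years | 13.7 (30-09-2023) |
| Belgium | 10.8 | 12.0 (31-12-2023) |
| NAJS | 5.8 | 6.9 (17-11-2023) |

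The figure reproduces for Germany, is borderline for Belgium to data lock, and clearly fails for NAJS.

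**2. Available window, if the search stops at study start.** The maximum look-back is index date minus database start. With index dates spread evenly (assumption), the mean is the midpoint of the range.

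| Database | Pre range (mean) | Post range (mean) | Ratio of means |
|---|---|---|---|
| Germany, starters from 2010 | 0 to 12.8 (6.4) | 13.1 to 13.7 (13.4) | 2.1 |
| Germany, starters from 2011 | 1.0 to 12.8 (6.9) | 13.1 to 13.7 (13.4) | 1.9 |
| Belgium | 1.0 to 10.8 (5.9) | 11.1 to 12.0 (11.5) | 2.0 |
| NAJS | 1.0 to 5.8 (3.4) | 6.1 to 6.9 (6.5) | 1.9 |

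Two German rows are needed because German records reach back before 2010. A starter in early 2010 can meet the 365-day rule and still have almost no look-back inside the study period.

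**3. Effect on the first-line share with no true change.** Assume recorded prior use accrues at a constant rate λ per year. The share is p = mean of exp(−λL) over the look-backs L, and SMD = (p₁ − p₂) / √{[p₁(1 − p₁) + p₂(1 − p₂)]/2}.

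Example, NAJS at λ = 0.05: p₁ = 0.845 and p₂ = 0.723, so SMD = 0.122 / √[(0.131 + 0.200)/2] = 0.30.

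For turnover, L is capped at 1 year plus an exponential time with mean 3, 5 or 10 years. The protocol gives neither λ nor the length of patients' history, so the ranges below are assumptions (λ = 0.02 to 0.10).

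| Database | SMD, full window | SMD, with turnover |
|---|---|---|
| Germany (both rows) | 0.28 to 0.64 | 0.05 to 0.33 |
| Belgium | 0.27 to 0.54 | 0.05 to 0.29 |
| NAJS | 0.19 to 0.41 | 0.08 to 0.30 |

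**4. The literal wording of section 8.8.** The earlier of study start and observation start is, in effect, each woman's whole recorded history. Section 8.2 dates German records from 1992. Using 1992 as the limit in the same model, the German SMD is 0.17 to 0.21 without turnover and 0 to 0.02 with it. Belgium and NAJS are unchanged, because they supply no earlier data.

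**5. Two remedies in the same model.**
- A fixed 365-day look-back gives p = exp(−λ) in both periods: 0.980, 0.951 and 0.905 at λ = 0.02, 0.05 and 0.10. The artefact is zero.
- Full history with pre-period starters limited to October 2021 to September 2022, against February 2023 to data lock, gives with turnover an SMD of about 0.02 or less in Germany, 0.03 or less in Belgium and 0.02 to 0.09 in NAJS.

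**The case against.** The strongest reply concerns size. Most patients do not stay in a database from its first day, and for them the window is set by their own history. For Belgium the protocol allows a rough check: 1.1 million cumulative patients against 213,000 active over 12 years suggests a mean tenure near 12 / (1,100/213 − 1) = 2.9 years under a steady-state assumption. The Belgian SMD is then 0.05 to 0.10. This stands: the full-window figures are an upper bound, and a reader should not infer that a large artefact is built into every database and every dose stratum. No calculation by dose stratum was made, and the literal German reading with turnover leaves almost nothing.

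Objective 4 is also descriptive. It has no test and no SMD threshold, and its hypothesis is worded as a number of first-line users rather than a share. A reader might infer that the hypothesis would be confirmed by artefact; the protocol sets no rule by which it would be confirmed. The share is nevertheless exposed, because the SMD compares the periods on line of treatment.

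Section 11 does disclose possible inaccuracy and the later database starts. A reader might infer that the 12-year statement is plainly wrong for two of the three databases; Belgium, at 12.0 years to data lock, is too close for that. What the disclosure lacks is that the error differs by period.

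Finally, a 365-day window relabels a woman treated 13 months earlier as first-line. That is a real cost, and it argues against making that window the only acceptable definition.

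**Conclusion.** The point holds as a design weakness in the pre/post comparison. Under the study-period reading in section 8.4 and section 11, the available look-back is about twice as long after the restrictions, and the first-line share is pushed down in the hypothesised direction. That direction follows from the protocol's dates and definitions if women have history to use and prior treatment accrues over time.

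The size does not follow from the protocol. For accrual of 2 to 10% per year, the spurious SMD is about 0.05 to 0.33 with turnover and 0.19 to 0.64 without. It is near zero in Germany with turnover if records before 2010 are used. The reassurance in section 11 does not hold for NAJS and does not address the difference between periods in any database. Separately, sections 8.4, 8.8 and 11 disagree on where the search ends, and section 8.4 differs from section 8.8 and the abstract on whether it includes the index day.

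**What to change.** Make the pre/post comparison of line of treatment rest on comparable look-back, in one of two ways:

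- **Same fixed window for every starter.** For example 365 days, which eligibility guarantees, plus a 3-year version in women who have that much history. This removes the artefact in the model above, but misses older treatments and so raises the first-line share in both periods.
- **Recent pre-period with full history, as in Objective 2.** October 2021 to September 2022, or February to July 2022 for the six-month version. This keeps older treatments and leaves only a small imbalance, largest in NAJS. It has fewer pre-restriction starters.

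Report the full-history, all-years result descriptively or as a sensitivity analysis.

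Reconcile the end of the look-back in section 8.8 with sections 8.4 and 11. If records from before the study period are not to be used, the limit is the later of study start and observation start. Align section 8.4 with the abstract and section 8.8 on excluding the index day. In section 11, give the available span by database and state that the misclassification differs by period.

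The cost is protocol wording plus one window or date parameter in the code; no new data are needed.
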